## 13.2 Endpoint analyses

## 13.2.1 Primary endpoint analysis

The primary endpoint is the proportion of women randomised who experience a live birth  $\geq$ 37 weeks. This proportion has as its denominator the number of women who are followed up after their ICSI cycle with first fresh embryo transfer post randomisation per arm and as its numerator the number of women who conceive and proceed to have a live birth  $\geq$ 37 weeks as

a result of their first fresh ICSI cycle. The proportion will be compared between arms using multivariable logistic regression adjusting for centre and for factors used in the minimisation. An odds ratio with 95% confidence interval will be calculated.

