## 5.4.4 Justification

- There is a need to increase LBR at term for IVF and IVF-ICSI patients by reducing fertilisation failure and miscarriage rate.
- Male fertility is thought to be declining through a reduction in sperm counts across the globe since WWII .

- The number of IVF and ICSI procedures is rapidly increasing and in particular, ICSI is being increasingly used for reasons other than treating male infertility (it now accounts for >50% of all IVF cycles), hence the selection of high quality sperm becomes a more urgent priority.
- Average LBR for IVF and IVF-ICSI have reached a plateau at 24% (although success rates vary widely across clinics and younger couples are generally more successful).
- Lower rates of fertilisation and higher rates of pregnancy loss following ICSI procedures are likely to generate higher costs as its use widens beyond treatment for male infertility. Wider use of ICSI without appropriate and adequate safeguards could lead to a future increase in the incidence of deleterious gene lesions in the wider population.
- The largest clinical trial so far, involving nine US centers has shown efficacy for PICSI in increasing CPR (10%) and a corresponding reduction in miscarriage rate (10%). A smaller Italian trial reported an encouraging 5% improvement in LBR following HA-based selection (using a non-optimised HA containing solution).
- Of the two commercially available HA-based selection systems, PICSI can be introduced into the ART procedure with minimal training and without any additional intervention and is the only product shown so far to have clinical efficacy in improving CPR.
- HA-based selection overcomes the highly subjective assessment of sperm quality used by the practicing embryologist to choose the 'right' sperm for injection.

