#### 10.5.1 Participant withdrawal before intervention

i.e. post enrolment and prior to randomisation will not receive the trial intervention and will resume standard treatment/care. Participants who withdraw prior to randomisation or trial intervention will be replaced with another couple on the trial.

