### **13. STATISTICAL CONSIDERATIONS**

The analysis will be by intention to treat. Every attempt will be made to gather data on all women randomised, irrespective of compliance with the treatment protocol.

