## 13.2.2 Secondary endpoint analyses

The secondary endpoints are the respective proportions of women who:

- experience a clinical pregnancy based on presence of fetal heartbeat or fetal sac at 6-9 weeks' gestation
- experience a clinical pregnancy and miscarry
- experience a clinical pregnancy and proceed to a live birth <37 weeks

These proportions have as their denominator the number of women who are followed up after their first ICSI cycle post randomisation, and as their numerator the number with the respective outcome. The proportions of each will be compared between arms using multivariable logistic regression adjusting for centre and for factors used in the minimisation. An odds ratio with 95% confidence interval will be calculated.

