## 13.6 Statistical Analysis

## 13.6.1 Clinical Evaluation

Our unit of analysis will be couples randomised to alternative interventions. In addressing the research question in this grant application, we have elected to focus on the outcome of the ICSI cycle with first fresh embryo transfer in each randomised couple and powered the trial accordingly. We believe that, if effective, the impact of the intervention will be evident in the first fresh study cycle. Attempting to evaluate cumulative live birth rates after an ICSI treatment culminating in transfer of fresh embryos followed by the subsequent transfer of frozen embryos in those not achieving a pregnancy would require an extended duration of follow-up. This would significantly increase the complexity and costs of the proposed trial, without generating outcomes of sufficient additional value.

Numbers of couples who are eligible, recruited, and followed up will be recorded in a CONSORT flow-chart. Baseline characteristics of couples in each arm will be tabulated. Outcomes in intervention and non-intervention arms will be compared using multivariable regression with effects summarised as odds ratios with 95% confidence intervals.

If there is evidence that the clinical pregnancy rate differs between the trial arms, then secondary analyses will be carried out taking only women with a clinical pregnancy as the denominator.

Sensitivity analyses will be carried out which adjust for other potentially prognostic factors in addition to the minimisation factors. Factors to be included will be selected blind to their distribution between recruitment arms or the effect of treatment on outcome, and will be those that are associated with the outcome or believed a priori to be prognostic.

In all cases, results of primary analyses will be given more weight than those of the secondary analyses.

**Subgroup analyses.** For binary outcomes, results will be expressed as odds ratio with 95% confidence intervals of pregnancy success in either arm. The exploratory subgroup analyses

- Hyaluronan Binding Score; HBS (High (>65%) versus low (≤65%)),
- maternal age (≤35 years versus >35),
- Previous miscarriages (none versus any),
- FSH hormone level (<6.0miU/ml versus ≥6.0miU/ml ) or AMH hormone level (<17pmol/L versus ≥17pmol/L) where FSH testing is not available.
- sperm concentration (<15mml versus ≥15mml).
- We may also analyse a very low (≤25%) vs. low (>25%, ≤65%) HBS sub-group.

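### Section 13.2.1 defines the primary endpoint among women randomised, then gives a denominator that, read literally, keeps only women who reached a fresh embryo transfer

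*Protocol*

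**What the plan says.** Section 13 sets the principle: "The analysis will be by intention to treat", and "Every attempt will be made to gather data on all women randomised, irrespective of compliance with the treatment protocol". Section 13.6.1 makes the randomised couple the unit of analysis. The first sentence of 13.2.1 takes the primary endpoint as a proportion of women randomised.

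The second sentence of 13.2.1 says that this proportion "has as its denominator the number of women who are followed up after their ICSI cycle with first fresh embryo transfer", counted per arm after randomisation. Its numerator is term live births from the first fresh ICSI cycle, with no mention of transfer. The outcome definition in 13.1.1.1 has no transfer condition either.

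For the secondary endpoints, 13.2.2 uses a different denominator: "the number of women who are followed up after their first ICSI cycle post randomisation".

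Two other rules bear on who is analysed. Under 10.5.1, whose opening words limit it to the time before randomisation, "Participants who withdraw prior to randomisation or trial intervention will be replaced with another couple on the trial". Under 13.6.1, if clinical pregnancy rates differ between arms, "secondary analyses will be carried out taking only women with a clinical pregnancy as the denominator".

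**The concern.** Women randomised and women followed up after a cycle that reached fresh transfer are different populations whenever some cycles do not reach transfer. The protocol expects such cycles: the Embryo Transfer CRF in 11.1.2 records whether zygotes formed and whether a transfer was done.

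The allocated procedure acts at sperm selection, upstream of fertilisation, embryo development and transfer. Section 5.4.4 says that live birth at term should be raised "by reducing fertilisation failure and miscarriage rate", and 5.3.2 cites better embryo grades with hyaluronan-selected sperm. An effect on who reaches transfer is therefore plausible. If there is one, an analysis restricted to transfers compares groups that randomisation no longer balances. A gain through better fertilisation would be partly removed from the result, and a loss through failed fertilisation would be partly hidden.

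The protocol fixes the primary denominator itself, in two incompatible ways, so this is not a detail left to a later analysis plan. Either denominator could be defended from the text after the data are seen.

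**Working it through.** **1. Order of events.** Randomisation is typically on the day of injection (9.5), after sperm preparation and before the sperm are processed by the allocated method (10.4). Zygotes are counted on Day 1 and transferred embryos on Day 2-5 (schedule in section 11; 11.1.2). Transfer comes after randomisation.

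**2. Populations named in the protocol.**

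| Place | Population or cycle |
|---|---|
| 13 | all women randomised |
| 13.6.1 | randomised couples |
| 13.2.1, first sentence | women randomised |
| 13.2.1, denominator | followed up after the cycle with first fresh transfer |
| 13.2.1, numerator | births from the first fresh ICSI cycle |
| 13.2.2, denominator | followed up after the first ICSI cycle |

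Of the two denominators, only the primary one mentions transfer.

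**3. The plan's own sample size.** Sections 13.4 and 13.5 give 3,266 couples for a 5-point improvement at 90% power. The overall control rate is not named there; 5.1 gives 24% per treatment cycle. Alpha is not stated; I assume two-sided 5%, in line with the 95% interval. With unpooled variances:

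n per arm = (1.960 + 1.282)² × (0.24×0.76 + 0.29×0.71) / 0.05² = 10.507 × 0.3883 / 0.0025 = 1,632.01, rounded up to 1,633; 2 × 1,633 = 3,266.

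This is an exact match, from a per-cycle rate. The calculation therefore fits an all-randomised denominator. After 10% loss, 3,730 × 0.90 = 3,357, and power for 24% v 29% is 90.7%.

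**4. Bias under the null (assumed transfer shares).** Let the true rate be 24% per randomised couple in both arms, with 1,865 per arm. If a share t reaches transfer, the rate among transfers is 0.24 / t.

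| Share reaching transfer, control v PICSI | Rate among transfers | Difference (points) | Odds ratio | Rejection at nominal 5% |
|---|---|---|---|---|
| 90% v 90% | 26.7% v 26.7% | 0 | 1.00 | 5.0% |
| 90% v 88% | 26.7% v 27.3% | +0.6 | 1.03 | 6.8% |
| 90% v 85% | 26.7% v 28.2% | +1.6 | 1.08 | 17% |
| 90% v 92% | 26.7% v 26.1% | −0.6 | 0.97 | 6.7% |
| 90% v 95% | 26.7% v 25.3% | −1.4 | 0.93 | 16% |

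Example: 0.24/0.85 = 0.2824; odds ratio = (0.2824/0.7176) / (0.2667/0.7333) = 1.08.

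**5. Distortion of a real effect.** With a true 24% v 29% per randomised couple, the difference among transfers is 0.29/t₁ − 0.24/t₀. It is 3.9 points at 90% v 95% and 7.5 points at 90% v 85%, against a true 5.

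**The case against.** The strongest reply is that the transfer wording names a cycle and does not filter women. The synopsis lists ICSI with first fresh embryo transfer as an inclusion criterion, although transfer cannot be known at entry. Section 7.3 speaks of randomised couples. Section 13.6.1 applies the phrase to each randomised couple and contrasts it with cumulative rates that include frozen transfers. On that reading the intended analysis is all randomised. This may well be what the authors meant. It does not rescue the text, because the denominator sentence does not say so and 13.2.2 leaves the phrase out.

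The missing-data rule in 13.3 does not help either: a couple with no transfer has a known outcome for that cycle, so nothing is missing.

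A reader might infer several stronger things that the documents do not support:

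- *That the trial has abandoned intention to treat.* The text contradicts itself; it does not settle on the restricted population.
- *That the protocol predicts an effect on fertilisation.* Section 5.4.4 states a general need for IVF and ICSI patients. Section 5.4.3 names less early pregnancy loss and a resulting rise in live birth as the main expected benefits.
- *That births from a later cycle would be counted.* The numerator limits births to the first fresh ICSI cycle.
- *That 10.5.1 removes randomised couples from the analysis.* It says that they are replaced, not excluded.
- *That the secondary endpoints switch to a pregnant-only denominator.* Those analyses in 13.6.1 are additional, and 13.2.2 still stands.
- *That the trial is underpowered.* If 90% reach transfer, 3,357 becomes 3,021, below 3,266, and power is 87.6% if 24% v 29% were per-transfer rates. But 24% is given per cycle. The rates among transfers would then be 26.7% v 32.2%, and power on 3,021 is about 92%.

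**Conclusion.** The point holds as a contradiction in the definition of the primary analysis population. Section 13.2.1 conflicts with its own first sentence, with section 13, with the unit of analysis in 13.6.1 and with the denominator in 13.2.2. Its literal rule conditions on a post-randomisation event and can bias the primary odds ratio in either direction.

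The size cannot be fixed from the protocol, which gives no transfer rates. Under the assumed shares, a 5-point gap between arms in reaching transfer moves the null odds ratio to about 1.08 or 0.93, a shift of roughly 1.5 points against a 5-point target. A 2-point gap moves it by about 0.6 points. Equal shares give no bias under the null. The sample size of 3,266 is not in question.

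The wording has to be corrected because it fixes who enters the primary test. The rules in 10.5.1 and the pregnant-only analyses are lesser matters to tidy at the same time.

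**What to change.** - **Denominator (13.2.1 and 13.2.2).** Define it as all couples randomised, by allocated arm, for the primary and all secondary endpoints.
- **No transfer.** Count a randomised cycle with no fertilisation or no fresh transfer as no live birth from that fresh cycle. Treat only truly unknown outcomes as missing.
- **Numerator.** Count only births from the fresh transfer of the randomised cycle. Births from later frozen transfers are not counted, in line with 13.6.1.
- **Per-transfer analysis.** It may be kept, labelled as secondary.
- **Withdrawals (10.5.1).** Reconcile the opening limit to the time before randomisation with the later mention of trial intervention, and state that couples already randomised stay in the analysis.
- **Pregnant-only analyses (13.6.1).** Report them as descriptive, because they are triggered when the arms differ in who becomes pregnant.

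The cost is a protocol wording change. The CRF already records fertilisation and transfer, and the required number stays at 3,266. The observed live birth rate will be somewhat lower in both arms than a per-transfer rate.

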## 13.2.2 Secondary endpoint analyses

The secondary endpoints are the respective proportions of women who:

- experience a clinical pregnancy based on presence of fetal heartbeat or fetal sac at 6-9 weeks' gestation
- experience a clinical pregnancy and miscarry
- experience a clinical pregnancy and proceed to a live birth <37 weeks

These proportions have as their denominator the number of women who are followed up after their first ICSI cycle post randomisation, and as their numerator the number with the respective outcome. The proportions of each will be compared between arms using multivariable logistic regression adjusting for centre and for factors used in the minimisation. An odds ratio with 95% confidence interval will be calculated.

#### 13.3 Handling missing data

Every attempt will be made to collect full follow up data on all couples and it is anticipated that missing data will be minimal. If baseline assessments of covariates are missing we will use mean imputation or missing value indicators to replace them . If any outcome data are missing we will analyse only those with outcomes data, adjusting for baseline covariates (this approach is unbiased if reasons for the outcome being missing can be related to observed covariates – the so-called "missing at random" assumption). We will also perform sensitivity analyses as suggested by White et al. .

#### 13.4 Sample Size – Clinical evaluations

From our study feasibility audit data, we estimate that around 4663 men per annum will be eligible for an ICSI procedure across all 10 participating centres and given our broad inclusion criteria, we conservatively expect 40% of the couples to meet eligibility and be willing to be consented to the study i.e. 3730 over 21 months. Trial recruitment is based on pro rata targets at each of the participating sites based on HFEA data and the need to recruit at least 3,266 couples into the trial to detect a 5% improvement in clinical efficacy.

For PICSI, average improvements in LBR per treatment cycle of 7.5% are likely based on maternal age and paternal semen profile ( $^{42, 48, 51}$ ). Older women ( $\geq$ 37) are of particular interest to us because their eggs may have a decreased capacity for the repair of sperm DNA damage

in their older partners . Lower and higher improvement scores among, respectively, younger and older women are likely. Assuming 5% for the former and 15% for the latter, rates will rise from 32.7% to 37.7% LBR (3826 treatment cycles) and 19.3% to 34.3% (358 treatment cycles) in women <35 and women >37, respectively. Because they lie between the more fertile younger and less fertile older age groups, improvements for women aged between 35 and 37 are likely to reflect that of women of all ages at 7.5%, we assume that miscarriage rate will be inversely correlated with LBR and therefore it is unnecessary to repower for it. Clearly, we shall have sufficient recruitment into the study to test outcomes in relation to HBS score predictions and parental age. However, lower improvement rates (among younger couples in particular) will incur lower accuracies unless power is relaxed to 80%. Improvement among older women is certainly testable, as those >37 now comprise almost 30% of ART procedures, providing 1007 women for the study.

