#### 13.5 Sample size - Mechanistic evaluation

The sample size for the clinical trial (3,730) is based on detecting a 5% improvement in live birth outcome at 90% power (3,266). In contrast, the mechanistic sample size is based on an estimated minimum of 180 required for logistic regression analysis of the relationship between HBS and clinical outcomes  and can therefore be far smaller. While this number accommodates the potentially limiting availability of samples with low (<50%) HB scores (estimated at ~10% or ~370), it is a minimum estimate that does not satisfy the need to more accurately specify the relationships between the mechanistic and clinical outputs of this study that are less dependent on HB scoring (such as sperm concentration). Furthermore, as indicated elsewhere, many of the samples will not be amenable to mechanistic tests. Hence, the chosen mechanistic sample size is a balance between minimum sample size requirements (180) required to link clinical and mechanistic outcomes, the need to access more samples in order to accommodate limitations in their use and the relative cost of analysis. Assuming that  $\sim$ 20% of samples can be examined by one or more tests based on cytology, only 36/180 will satisfy the criteria. Hence ~900 samples (180/36\*180) are required overall. All mechanistic tests are needed to facilitate the identification of the form of damage that compromises sperm function in relation to clinical outcome (Fig 6).

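### Relaxing power to 80% does not make a 5-point gain testable in women under 35: about 2,857 cycles are needed, and the protocol's own figures supply fewer even with no loss to follow-up

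*Protocol*

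**What the plan says.** Section 13.4 sets out expected gains by maternal age. For women under 35, "rates will rise from 32.7% to 37.7% LBR (3826 treatment cycles"). For women over 37 the rise is "19.3% to 34.3% (358 treatment cycles) in women <35 and women >37, respectively". Women aged 35 to 37 are treated as a separate middle group with an intermediate gain.

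The section then concludes: "Clearly, we shall have sufficient recruitment into the study to test outcomes in relation to HBS score predictions and parental age". The next sentence qualifies this for smaller gains: "lower improvement rates (among younger couples in particular) will incur lower accuracies unless power is relaxed to 80" per cent. Older women are said to be testable, "as those >37 now comprise almost 30% of ART procedures, providing 1007 women for the study".

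The totals are given elsewhere. The recruitment target is 3,730 couples (section 9.1), and 3,357 outcomes remain after a 10% loss that the protocol calls the worst case (section 13.4.1). Section 13.5 says the clinical sample size "is based on detecting a 5% improvement in live birth outcome at 90% power (3,266"). Section 13.6.1 lists maternal age among the exploratory subgroups, with an interaction test to come first.

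**The concern.** The requirement printed for women under 35 is larger than the whole trial, yet the same paragraph concludes that recruitment is sufficient to examine parental age. The only relief offered for younger couples is a lower power of 80%. A reader will take this to mean that a 5-point gain in women under 35 can be tested at 80% power. If the numbers do not support that, the protocol credits a subgroup with a power it does not have, and an inconclusive result in younger women could later be given more weight than it deserves.

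**Working it through.** **Inputs**
- Live birth rates: 32.7% v 37.7% (under 35) and 19.3% v 34.3% (over 37), section 13.4.
- Allocation 1:1, section 9.5.
- Power: 90% by design (section 13.5); 80% as the relaxed value (section 13.4).
- Significance level: not stated for the sample size. Two-sided 5% is assumed, in line with section 13.2.1: "An odds ratio with 95% confidence interval will be calculated".
- Totals: 3,730 recruited; 3,357 after 10% loss; 1,007 women over 37.

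**Step 1. Reproduce the protocol's figures.** Two proportions, unpooled variance, per arm:

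n = (z₁₋α/₂ + z_power)² × [p₁(1−p₁) + p₂(1−p₂)] / (p₁−p₂)²

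For women under 35 the variance sum is 0.327×0.673 + 0.377×0.623 = 0.4549, and 0.4549/0.05² = 181.98. At 90% power, (1.960+1.282)² = 10.51. That gives 1,913 per arm after rounding up, or **3,826** in total, an exact match. A one-sided 5% test gives about 3,118 to 3,202 and does not match.

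The same formula gives 356 for women over 37 (stated 358). It gives 3,266 for 24% v 29% (stated 3,266), with the 24% taken as an assumption from the average rate in sections 5.1 and 5.4.4. The method is therefore identified.

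**Step 2. Requirement at 80% power.** (1.960+0.842)² = 7.85, and 7.85 × 181.98 = about 1,428 per arm, so about **2,857** in total (2,858 in whole arms). A pooled-variance formula gives 2,864; with continuity correction it is 2,942.

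**Step 3. Women available.** The 1,007 women over 37 are 30% of 3,357. Women aged 37 or under are the remainder. The power column is for 32.7% v 37.7%, two-sided 5%, pooled variance under the null.

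| Basis | Aged 37 or under | Power |
|---|---|---|
| 10% loss: 3,357 − 1,007 | 2,350 | 71.8% |
| No loss: 70% of 3,730 | 2,611 | 76.3% |
| No loss, most generous: 3,730 − 1,007 | 2,723 | 78.0% |

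Each count is below 2,857, and each still contains women aged 35 to 37, who must be removed to reach the under-35 group.

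**Step 4. Illustration for women under 35.** The protocol gives no share for this group. If it were 40% to 50% of 3,357 (an assumed range), the number would be 1,343 to 1,678 and power 48% to 57%.

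**Step 5. Sensitivity to the 30% share.** With no loss, 2,857 is 2,857/3,730 = 76.6% of the trial. Women over 37 would have to be no more than 23.4%, and nobody could be aged 35 to 37. With 10% loss the limit is 1 − 2,857/3,357 = 14.9%.

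**Step 6. Women over 37.** 358 are needed and 1,007 expected; power exceeds 99%. That statement is right.

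**The case against.** Several objections deserve weight.

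- *The sentence is a caveat.* It concedes lower accuracy for younger couples and never says outright that women under 35 will have 80% power. That is fair, and it narrows the point: what fails is the implied remedy, together with the unqualified sufficiency claim just before it.
- *The figure of 2,350 assumes the worst-case loss.* This stands. A reader might take 2,350 women and 72% power as hard maxima. They are not, because section 13.4.1 expects follow-up to be better than that. The no-loss counts of 2,611 to 2,723 are the proper ceiling, and they also fall short.
- *The 30% refers to assisted reproduction procedures, not to this trial.* True, but it is the protocol's own working share, and step 5 shows how far it would have to move.
- *A one-sided test would fit.* At 80% power it needs about 2,252, fewer than 2,350. But the printed 3,826 reproduces only as two-sided, and the 2,350 still includes ages 35 to 37.
- *The subgroups are exploratory.* Section 13.6.1 puts an interaction test first, limits subgroup results to hypothesis generation and cuts maternal age at 35, not at under 35 and over 37. A reader might infer that the trial is heading for a false claim that only older women benefit. The existing rule guards against setting one group's null result beside another's positive one, so the documents do not support that inference. The rule does not, however, correct a wrong statement about power.

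**Conclusion.** The point holds, within limits. On the protocol's own rates and counts, a 5-point gain in women under 35 cannot be tested at 80% power. The need is about 2,857 cycles, against fewer than 2,350 women after 10% loss and fewer than 2,611 to 2,723 with none. Power is therefore below about 72% and below about 76% to 78% respectively, and lower again once ages 35 to 37 are taken out. This rests on a two-sided 5% test, which the printed 3,826 confirms, and on the protocol's 30% share over 37.

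A reader might go on to infer that the trial itself is underpowered. It is not on these figures: the whole-trial comparison needs 3,266 and 3,357 are expected after loss. Nor can a single power figure such as 50% to 60% be put on women under 35, because that depends on an age share the protocol does not give. The error is one of statement, confined to younger women.

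**What to change.** Revise section 13.4 as follows:

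1. Limit the sufficiency sentence so that, for maternal age, it does not cover women under 35.
2. Withdraw the implication that 80% power is achievable in that group.
3. State the deliverable position, for example: *In women under 35, a gain from 32.7% to 37.7% would need about 2,857 cycles for 80% power (two-sided 5%). Fewer are expected even with no loss to follow-up, so power will be below 80%: below about 72% with 10% loss, and lower once women aged 35 to 37 are excluded.* If a figure for the group itself is wanted, give 48% to 57% only as an illustration, with the assumed share of 40% to 50% of 3,357 stated beside it.
4. Refer to the exploratory, interaction-first rule in section 13.6.1. No new rule is needed.
5. Leave the statement for women over 37 as it is.

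The cost is wording only. Sample size, eligibility and analyses do not change; the stated power for younger women becomes less favourable.
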